10.3. Targeted Adverse Events- Local Skin Reactions

Local skin reactions (LSRs) to treatment reported by investigators and subjects will be recorded as adverse events. Two questions on the adverse event form are “Is this Adverse Event at a location where study drug was administered?” and “Did event occur during the paring procedure?” If the answer is Yes to the location question and No to the

paring procedure question, the adverse event will be considered a Local Skin Reaction. LSRs will be coded and summarized using similar methods as described in Section 10.2 for adverse events.

Summaries of LSRs will include the following:

- Subject count and incidence rate of LSRs by MedDRA system organ class and preferred term.
- Subject count and incidence rate of LSRs by MedDRA preferred term and highest severity. At each level of subject summarization, a subject is classified according to the highest severity if the subject reported one or more events.
- Subject count and incidence rate of LSRs by MedDRA preferred term and closest relationship to study drug (Related/Not Related). Related LSRs are those reported as “Definitely”, “Probably” or “Possibly”. At each level of subject summarization, a subject is classified according to the closest relationship if the subject reported one or more events. LSRs with missing relationship will be considered related for this summary.
- Subject count and incidence rate of serious LSRs by MedDRA system organ class and preferred term.
- Subject count and incidence rate of LSRs by study specific LSR categories. Mapping of LSRs will be done via a medical review. Possible categories of LSRs will include the following: Blistering, Pain, Pruritus, Erythema, Edema, Erosion/Ulceration, Flaking/Scaling/Dryness, Scabbing/Crusting, Pigmentation Changes.

Adverse events that appear at a location where drug was administered and occur during the paring procedure will not be considered LSRs. A separate summary table will be generated to summarize those adverse events that meet these conditions (i.e., the answer is Yes to the location question and Yes to the paring procedure question, therefore the adverse event will be considered as related to the paring procedure and not an LSR).

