4.3.1 Safety

All subjects who meet the screening eligibility criteria for the study and receive at least one application of Study drug will be evaluated for safety. The following safety parameters will be assessed:

- Incidence of adverse events (AEs) throughout the study:
 - A subject-by-subject AEs data listing, including verbatim term, preferred term, treatment, severity, location and causal relationship to the Study drug, will be provided.
 - The number of subjects experiencing treatment emergent Adverse Events (TEAEs) and number of TEAEs will be summarized by treatment using frequency counts.
 - AEs will include all local skin reactions whether or not they are expected or related to Study drug mechanism of action.
- LSRs of all previously treated areas will be assessed at each Treatment Visit using the protocol specific ERT form.
 - Subjects will have reviewed and be given take home instructions on removal of the occlusive tape and also descriptions of the potential local skin reactions they might expect throughout the course of the study. Recommendations for wound care, when it is important to call their doctor, and instructions for whom to contact in an emergency are also included.
 - ERT assessments will be conducted at each Treatment Visit 1-4, in-person, prior to re-treatment. ERT phone calls will also be conducted at 24 hours and 7 days after Treatment Visits 1-4 to confirm removal of the occlusive tape, assess treatment response, document any local skin reactions and any medical interventions taken. ERT assessments will be conducted whether or not treatment is applied. Cohort 1 subjects that exhibit complete clearance prior to EOS, will not be required to return to the clinic until EOS Day 84. ERT phone calls will be scheduled and conducted at each two-week treatment interval until the in-person EOS visit or the subject reports recurrence or new warts that require an in-person assessment and treatment. Cohort 2 subjects will be required to return for each Treatment Visit until EOT as well as Follow-up Visits on Day 105, 126 and 147.
 - A LSR Guide for subjects with specific photos identifying the various skin reactions and examples of intensity will be reviewed at the clinic with the subject/guardian by the research team. This guide will be utilized for discussion during the ERT phone

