7.4 Assessment of Intensity

The investigator will assess the intensity for each AE and SAE reported during the study. The assessment will be based on the investigator's clinical judgment.

The classifications in Table 3 should be used in assigning intensity of each AE recorded in the eCRF.

Table 3 Classification of AEs by Intensity

Intensity	Definition
Mild AE	An event that is easily tolerated by the subject, causing minimal discomfort and not interfering with everyday activities
Moderate AE	An event that is sufficiently discomforting to the extent of interfering with normal everyday activities
Severe AE	An event that prevents the subject from performing normal everyday activities

AE: adverse event.

Any AE that changes in intensity during its course will be recorded in the eCRF at the highest level experienced by the subject.

An AE that is assessed as severe should not be confused with an SAE. Severity is a category used for rating the intensity of an AE (such as mild, moderate, or severe myocardial infarction). However, the event itself may be of relatively minor medical significance, such as a severe headache. Both AEs and SAEs can be assessed as severe. An AE is considered serious (an SAE) when it meets one of the predefined outcomes described in Section 7.2.

Local Skin Reactions should be rated based on the severity ratings in the Local Skin Reaction Guide that is provided.

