9.2.4 Safety Analysis

Safety analysis will be based on the safety population. Subjects will be assigned to the treatment received for any analysis of safety.

Adverse event data for the safety population will be listed individually, and the incidence of adverse events will be summarized by treatment, System Organ Class, and Preferred Term using frequency counts. LSRs will also be tracked by the incidence of subjects with each LSR and the maximal intensity throughout the study. These will be tabulated by total rate of occurrence and rate of severe occurrences. When calculating the incidence of adverse events, only Treatment Emergent Adverse Events (TEAEs) will be considered. In addition,

any adverse event with an onset date after the EOS visit will be considered off study and will not be included in tables summaries (though they will appear in adverse event listings). Each adverse event will be counted only once for a given subject. If the same adverse event occurs on multiple occasions for a subject, the occurrence with the highest severity and relationship to Study drug will be reported. If two or more adverse events are reported as a unit, the individual terms will be reported as separate events. Changes in vital signs, from baseline to the end of the study will be examined. Treatment-emergent changes from normal values to abnormal values will be identified as described in Section 4.3.1.

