10.2. Adverse Events

Adverse events summaries will only consider TEAEs. TEAEs are defined as those adverse events that occurred after dosing and those existing adverse events that worsened during the study. If it cannot be determined whether the adverse event is treatment emergent due to an incomplete (partial) onset date, the adverse event will be considered to be treatment emergent. Adverse events with an onset day after the EOS visit will be included in listings but not considered TEAEs; therefore, such adverse events will not be considered for table summaries. Verbatim terms entered into the clinical database via the EDC system will be mapped to preferred terms and system organ classes using version 20.0 of Medical Dictionary for Regulatory Activities (MedDRA).

Each adverse event summary will be displayed by treatment group. Summaries that are displayed by system organ class and preferred terms will be ordered by descending order of incidence of system organ class and preferred term within each system organ class. Summaries of the following types will be presented:

- Overall summary of the TEAEs which contain an overview of each item below.
- Subject count and incidence rate of TEAEs by MedDRA system organ class and preferred term.
- Subject count and incidence rate of TEAEs by MedDRA preferred term and highest severity. At each level of subject summarization, a subject is classified according to the highest severity if the subject reported one or more events.
- Subject count and incidence rate of TEAEs by MedDRA preferred term and closest relationship to study drug (Related/Not Related). Related AEs are those reported as “Definitely”, “Probable” or “Possibly”. At each level of subject summarization, a subject is classified according to the closest relationship if the subject reported one or more events. Adverse events with missing relationship will be considered related for this summary.
- Subject count and incidence rate of Serious TEAEs by MedDRA system organ class and preferred term.
- Subject count and incidence rate of TEAEs leading to withdrawal of study medication by MedDRA system organ class and preferred term.

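### SAP 10.3 takes every treated-site event flagged as occurring during paring out of the local skin reaction tables, even if rated related to VP-102 or worse after application, so Cohort 2 LSR incidence and severity can be understated

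*SAP*

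**What the plan says.** SAP 10.3 uses two questions on the adverse event form. An event counts as an LSR only if it lies where drug was administered and the answer to "Did event occur during the paring procedure" is No. If both answers are Yes, the rule is categorical: "Adverse events that appear at a location where drug was administered and occur during the paring procedure will not be considered LSRs". The SAP then assigns the cause: "therefore the adverse event will be considered as related to the paring procedure and not an LSR". These events get their own output: "A separate summary table will be generated to summarize those adverse events that meet these conditions".

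Three other provisions bear on the rule.

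- Protocol 7.4, on recording: "Any AE that changes in intensity during its course will be recorded in the eCRF at the highest level experienced by the subject". It does not ask for a new record when an event worsens.
- SAP 10.2, on treatment emergence: "TEAEs are defined as those adverse events that occurred after dosing and those existing adverse events that worsened during the study". It has no paring exclusion, and it tabulates events by highest severity and by reported relationship to study drug. Missing relationship counts as related.
- Protocol 9.2.4, on LSR analysis: "LSRs will also be tracked by the incidence of subjects with each LSR and the maximal intensity throughout the study". It also tabulates the rate of severe occurrences and makes no exception for paring.

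Protocol 4.3.1 takes a broad view of capture: "AEs will include all local skin reactions whether or not they are expected or related to Study drug mechanism of action".

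**The concern.** In Cohort 2, paring is done before VP-102 is applied to the same wart. A single yes/no answer about timing decides whether the whole record is a drug-site reaction or a procedural event. The SAP does not say what happens when an event straddles the two. It also lets the timing answer stand in for the causality judgement that Protocol 7.5 requires of the investigator.

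Safety and tolerability, including expected LSRs, is a primary objective for Cohort 2. The LSR tables are its main treated-site summary, because SAP 10.4 plans no separate table for the evaluation of response to treatment (ERT). The exclusion can only take records out of these tables. Any misclassification that it causes therefore makes the drug look better tolerated.

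**Working it through.** The documents give no LSR rate and no power figure for this point, so there is no planned number to reproduce. The check traces the rule and then sizes it under stated assumptions.

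**1. Trace of four kinds of treated-site record in Cohort 2**

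| Record | General TEAE tables (SAP 10.2) | LSR tables (SAP 10.3) | Paring table (SAP 10.3) |
|---|---|---|---|
| A. Confined to paring, rated unrelated | Yes, if after first dose | No | Yes |
| B. Starts at paring, worsens after drug, one record, rated related | Yes, at peak severity, as related | **No** | Yes |
| C. Post-drug reaction entered as its own record | Yes | Yes | No |
| D. As B, but rated unrelated | Yes, at peak severity, as not related | No | Yes |

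Row A is sensible and row C loses nothing. Row B is the fault: the same record is drug-related in one table and deemed paring-related in another, and its post-drug peak is missing from LSR severity. Row D can also hold a post-drug peak, but there the exclusion agrees with the investigator.

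Overlap is foreseeable for pain. SAP 3 says that paring is to stop if it causes significant pain, and pain is one of the SAP 10.3 LSR categories.

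**2. Fixed quantities**

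- Cohort 2 has about 35 subjects and up to 4 treatments each (SAP 3).
- Ceiling on paring-plus-application occasions: 35 × 4 = 140. The true number is lower, because not every wart needs paring and sites that stay clear are not re-treated.
- One subject: 1/35 = 2.9 percentage points.

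**3. Illustration of the loss in subject incidence**

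Let k be the number of treatment visits, p the chance per visit of a drug reaction in one LSR category, and m the chance that this reaction sits on a record flagged as paring. Visits are taken as independent. Both p and m are assumptions; the documents give neither.

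- True incidence = 1 − (1 − p)^k
- Tabulated incidence = 1 − (1 − p(1 − m))^k

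Worked case, k = 4, p = 0.3, m = 0.20: true = 1 − 0.70⁴ = 76.0%; tabulated = 1 − 0.76⁴ = 66.6%. The loss is 9.4 points, or 3.3 of 35 subjects.

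| k | p | Loss at m = 0.05 | m = 0.20 | m = 0.50 |
|---|---|---|---|---|
| 4 | 0.1 | 1.5 | 6.0 | 15.8 |
| 4 | 0.3 | 2.1 | 9.4 | 28.2 |
| 4 | 0.9 | 0.0 | 0.6 | 9.1 |
| 1 | 0.3 | 1.5 | 6.0 | 15.0 |
| 1 | 0.9 | 4.5 | 18.0 | 45.0 |

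(Percentage points. At m = 0 the loss is 0 in every row.)

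**4. What the table shows**

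A subject leaves a category only if every event in it is flagged as paring. Repeated visits therefore protect the incidence of common reactions: at k = 4 and p = 0.9, the loss is at most 0.6 points for m up to 0.20. Severity is less protected. A subject can stay in the incidence count through a milder record and still lose the severe one. If severe reactions are rarer, the low-p rows apply to them: at k = 4, p = 0.1, m = 0.20, incidence falls from 34.4% to 28.4%.

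**5. Treatment Visit 1**

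Paring at this visit comes before the first dose, so under SAP 10.2 an event then is treatment-emergent only if it worsens. Such a record enters the TEAE tables because it worsened, and SAP 10.3 still denies it LSR status.

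**The case against.** The strongest reply is that the rule is reasonable and nothing is hidden. Most of its parts stand.

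- **Separation is proper.** Counting every paring injury as an LSR would overstate drug reactions.
- **The events stay visible.** They have their own summary table. If treatment-emergent, they remain in the TEAE tables by severity and by the investigator's rating. The by-subject listing carries severity, location and causality.
- **Post-drug reactions have their own capture routes.** Protocol 6.2.3 records adverse events before and after application. Under SAP 10.4, symptoms reported at the clinic, 24-hour and 7-day ERT go on the adverse event form. A new reaction found there would be answered No for paring and counted as an LSR.
- **Drug pain may start later.** Protocol 2.2 describes application as painless, and one published wart study in Protocol 2.2.2 warned of pain from 6 to 8 hours after application. On that account, paring pain and drug pain would often be distinct.
- **The definition is otherwise generous.** Any other treated-site event is an LSR whatever its rated cause.

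A reader might infer that Cohort 2 drug reactions are in fact understated, that these events disappear from safety reporting, or that VP-102 follows paring within minutes so that one record is inevitable. The documents support none of these. The understatement depends on site recording practice, the events are tabulated elsewhere, and no interval between paring and application is given.

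The reply does not reach row B. Nothing in these sections requires a separate record after drug, and Protocol 7.4 points towards a single one. The general TEAE tables do not isolate treated sites, and the paring table labels the event as procedural. Neither puts it back into the LSR summary.

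**Conclusion.** The point holds as a rule that can misclassify, not as a demonstrated bias. SAP 10.3 excludes paring-flagged events from the LSR tables even when the investigator attributes them to VP-102 and even when their recorded peak came after application. With Protocol 7.4, this can understate LSR incidence and, more readily, LSR severity, mainly for pain.

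The amount runs from nil to material, and the documents cannot narrow it. It depends on whether sites keep one record across paring and drug exposure. Every figure above other than 35, 4, 140 and 2.9 points rests on assumed p and m and on independent visits. The study is open-label and descriptive, and the complete-clearance endpoint is untouched. The correction is still worthwhile, because tolerability is a primary objective and the exclusion can err in only one direction.

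**What to change.** In SAP 10.3:

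1. Exclude a treated-site event with paring answered Yes from the LSR tables only if the investigator rated it unrelated to study drug. Count those rated definitely, probably or possibly related as LSRs at their recorded highest severity. Treat a missing relationship as related, as SAP 10.2 and 10.3 already do in the relationship summaries. Keep all paring-flagged events in the paring table as well.
2. Add one sensitivity LSR table, by incidence and highest severity, that counts all treated-site TEAEs whatever the paring answer. This brackets the effect of the rule and covers row D.

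Both changes use fields already collected. Two other routes are less workable. An end-date condition cannot show that an event resolved before drug was applied at the same visit. A new record on worsening would depart from Protocol 7.4, and without one only the overall peak severity is stored.

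The cost is a revised sentence, one programming condition and one extra table. Some paring-only discomfort may be counted as LSR, which makes the tolerability figure slightly less favourable; the paring table still shows those events.

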10.4. Evaluation of Response to Treatment (ERT)

For each treatment visit, an Evaluation of Response to Treatment (ERT) will be performed (in clinic) and 24 hours and 7 days post treatment (by phone). The ERT contains questions about experiences related to treatment, such as blistering and pain. Should any symptoms be reported as part of the ERT, those symptoms will be recorded on the adverse event form. Therefore, no ERT specific table summary will be generated. Any additional information collected on the ERT will be presented in listings.

10.5. Provider Questionnaire

At the EOT visit for Cohort 2, a 9-question Provider Questionnaire will be completed. Questions will include ease of use of the applicator and general experiences. Responses to the questions will be displayed in subject listings. No summary tables of the questionnaire are planned.

10.6. Vital Signs

Heart rate and temperature will be collected at each visit. Change from baseline will be calculated for each post baseline visit temperature and pulse rate. Weight and height will be collected at baseline and at the EOS visit.

Summary statistics for each vital sign and change from baseline result will be displayed by treatment group and visit for temperature and pulse rate. Baseline height and weight will be summarized as part of the baseline summary. Any other collection of height and weight will be included in by subject listings.

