- b. Subjects are to be scheduled in 21-day intervals (+/- 4 days) after each treatment for subjects in Cohort 2. The next Treatment Visit is to be scheduled 21 (+/- 4 days) after the last treatment, but only after any LSR has resolved sufficiently to allow evaluation of the treatment site. The research team should be in contact with the patient until LSRs are resolved and a treatment visit can be scheduled within 21 days (+/- 4) when possible. The 24-hour phone contact may be conducted at +/- 6 hours. The 7-day phone contact may be conducted +/- 24 hrs.
- c. A final in person safety assessment, ERT, photos and study completion form will be completed at the Day 147 (EOS) Visit for all subjects. EOS conducted outside the Day 147 EOS visit window will be considered a protocol deviation. Treatments may be administered up to Day 75 in Cohort 2. Subjects in Cohort 2 are to attend all visits whether they have achieved complete clearance prior to and at the Day 84 (- 0/+ 8 days) EOT assessment.
- d. Demographics: date of birth, sex, race/ethnicity will be collected.
- e. Vital signs (e.g., temperature & heart rate) will be obtained at each treatment prior to application of Study drug. Height and weight will be collected at Screening/Day 1, EOT Day 84 (- 0/+ 8 days) and subsequent follow up visits Day 105, 126 and 147 (EOS).
- f. Limited physical examination. Symptom or AE-directed physical examination may be performed if warranted. (See Source/eCRF for a more detailed description)
- g. Dermatologic exam including Fitzpatrick Skin Type, location of each wart is identified and documented on the body map and source as outlined in the MOP. Measurements of warts should be recorded on Day 1 prior to treatment to confirm they meet inclusion criteria of ≤ 10 mm in diameter and ≤3 mm in height. Wart location, measurements and assessments are to be completed prior to each treatment application and/or each in-person visit. New warts should be recorded in the corresponding Source/eCRF. Instructions for measuring and documenting the and measurements are provided in the Manual of Operations.
- h. Paring at first visit by Dermatologist or qualified designee. Paring at additional treatment visits if significant hyperkeratosis or at Investigator’s discretion.

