On the Wart Location and Measurement case report form (CRF), wart information is collected for each individual wart. For the purpose of efficacy analysis, clearance of each wart needs to be determined using results collected on this page. A wart will be considered to have cleared for a particular visit when a wart is reported to have a diameter of 0 mm at that visit. Should a wart return after initial clearance, a diameter > 0 mm will be recorded, and the wart will not be considered cleared at that visit. Otherwise,

if the wart does not return, the check box “Wart has cleared” will be marked for subsequent visits. For the purpose of analysis, the wart will be counted as cleared at all visits where “Wart has cleared” has been marked.

Some efficacy endpoints will be summarized by treatment visit. Treatments are planned to occur every 21 days as long as warts are present for up to 4 treatments within the 75 day treatment period. Treatment may be delayed for various reasons including, but not limited to, ongoing local skin reactions (e.g. scabbing). As a result, the timing of when subjects receive treatment may vary. For the purpose of naming treatment visits, only visits when treatment was given or the check box “Wart has cleared” for all warts will be considered. Using this method, Treatment Visit 1 will be the 1st visit treatment was applied; Treatment Visit 2 will be the 2nd visit treatment was applied, etc. Visits when treatment was planned to be given but treatment was not applied or clearance was not achieved will be recorded as “Unscheduled”.

For results to be considered for any by visit analyses, visits must be within visit windows as described in this section of the analysis plan. Results that are collected between Day 11 and Day 157 will be assigned to visits according to the visit windows described below, regardless of the name of the visit. Should two or more results be collected within a specific visit window, the visit closest to the planned day with a non-missing value will be used for analysis. Results from visits that occur outside the visit windows will not be considered for analysis, but will be included in study listings. The visit windows to be considered are as follows:

- Day 21- visit falls +/- 10 days from planned visit study day (i.e., between Day 11 and Day 31)
- Day 42- visit falls +/- 10 days from planned visit study day (i.e., between Day 32 and Day 52)

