9.4. Reduction of Wart Area

At each treatment visit, the EOT visit and each follow-up visit, the maximum diameter of each wart will be measured. The area of each wart will be estimated assuming the shape of the wart is a circle. Thus, the area of each individual wart will be calculated using the formula:

$$\text{Area of Individual Wart} = \pi * \left(\frac{\text{Diameter of Individual Wart}}{2}\right)^2$$

Where π = the constant 3.14. At each treatment visit and the EOT visit, the total wart area will be determined for the subject by summing the areas of the individual warts estimated at that visit. The change and percent change in wart area will be calculated for each treatment visit and the EOT visit and will be summarized using summary statistics. The percent change will be calculated using the same formula described in Section 9.2 (using wart area rather than number of warts).

An additional set of analyses will include reporting the number and percent of subjects with a $\geq 50\%$ reduction in total wart area from baseline to the EOT visit. Subjects with a $\geq 50\%$ reduction from baseline in total wart area will be considered to have responded to treatment.

10. Safety Analysis

All safety analyses will be based on the Safety Population. For any by visit analyses to be carried out, visit windows discussed in Section 8 will be applied to safety data.

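### SAP 10.6 omits the normal-to-abnormal vital-sign analysis that protocol 9.2.4 promises, and the efficacy visit windows keep Day 2-10 readings out of the vital-sign table

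*SAP*

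**What the plan says.** **Promised analysis.** Protocol 9.2.4 (Safety Analysis), directly after saying that changes in vital signs will be examined, states: "Treatment-emergent changes from normal values to abnormal values will be identified as described in Section 4.3.1".

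**SAP analysis.** SAP 10.6 provides by-visit tables only, for pulse and temperature: "Summary statistics for each vital sign and change from baseline result will be displayed by treatment group and visit".

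**Windows.** SAP Section 10 says: "For any by visit analyses to be carried out, visit windows discussed in Section 8 will be applied to safety data". Section 8 sets these windows at the planned day plus or minus 10 days. "Results that are collected between Day 11 and Day 157 will be assigned to visits". An unscheduled visit is handled like any other, since the assignment is made "according to the visit windows described below, regardless of the name of the visit". If a window holds several results, "the visit closest to the planned day with a non-missing value will be used for analysis". Also, "Results from visits that occur outside the visit windows will not be considered for analysis"; they go to listings.

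**Collection.** Protocol Table 2, footnote e (Cohort 2): "Vital signs (e.g., temperature & heart rate) will be obtained at each treatment prior to application of Study drug". The Table 2 grid marks vital signs at unscheduled visits and leaves the Day 105, 126 and 147 follow-up visits blank. Protocol 6.2.4 does not list vital signs among unscheduled-visit procedures, while 6.2.6 does list them for the follow-up visits.

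**The concern.** Two separate gaps meet in the same table.

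The first is a protocol commitment with no counterpart in the SAP. A programmer following the SAP would produce no count of subjects who moved from normal to abnormal. A programmer following the protocol could not produce one either, because no limits are given.

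The second is timing. Vital signs at treatment visits are taken before the drug goes on, so on the planned schedule they fall 17 to 25 days after the previous application. Readings in the first days after an application come mainly from unscheduled visits, if vital signs are taken there. Subjects who report excessive blistering, ulceration, edema or pain are called to those visits. Windows chosen for efficacy timing keep one reading per window and prefer the one nearest the planned day, which is usually the pre-application reading.

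What is at stake is a planned safety result. Safety and tolerability form one of the two primary objectives of Cohort 2, although vital signs are not among the measures named in that objective.

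**Working it through.** **1. The two documents side by side**

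| Item | Protocol | SAP |
|---|---|---|
| Change in vital signs from baseline | 9.2.4: examined | 10.6: summarised by visit |
| Normal-to-abnormal changes | 9.2.4: will be identified | none |
| Normal limits for heart rate and temperature | none in 4.3.1, the section cited | none |

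Section 4.3.1 says when vital signs are taken, not what counts as abnormal. This result needs no arithmetic and no assumption.

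**2. The windows, reproduced**

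The planned day plus or minus 10, for planned Days 21, 42, 63, 84, 105, 126 and 147, gives Days 11-31, 32-52, 53-73, 74-94, 95-115, 116-136 and 137-157. These match SAP Section 8. They are contiguous and begin at Day 11, so no window contains Days 2-10, that is, the 1 to 9 days after a Day 1 application.

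**3. Selection rule for later readings**

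Take an unscheduled reading on day u = T + k, that is, k days after an application on day T. It lies in the window with planned day p. It is tabulated only if |u - p| is smaller than |s - p| for every scheduled reading s in that window.

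- On schedule: application on Day 22, reading on Day 24. |24 - 21| = 3 and |22 - 21| = 1, so the treatment-visit reading is used.
- Early visit: application on Day 18, reading on Day 20. |20 - 21| = 1 and |18 - 21| = 3, so the unscheduled reading is used and replaces the treatment-visit reading.

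**4. Exact schedule**

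With applications on Days 1, 21, 42 and 63, there are 4 applications x 10 days (k = 1 to 10) = 40 combinations, and 0 are selected. With applications on Days 1, 22, 43 and 64, again 0 of 40.

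**5. Permitted drift**

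Inputs from the protocol: intervals of 21 plus or minus 4 days (17 to 25), applications up to Day 75, EOT on Day 84. Assumptions of this check: the 9 x 9 x 9 = 729 interval combinations are equally likely, reading days are equally likely, and every scheduled reading is present. A reading must precede the next scheduled visit, and ties go to the scheduled visit.

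| Days after application | Appl. 1 | Appl. 2 | Appl. 3 | Appl. 4 | All |
|---|---|---|---|---|---|
| 1-3 | 0% | 25.9% | 29.3% | 32.4% | 1916/8745 = 21.9% |
| 1-7 | 0% | 14.3% | 23.4% | 25.1% | 3202/20405 = 15.7% |
| 1-10 | 0% | 10.9% | 21.2% | 20.7% | 3837/29138 = 13.2% |

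If ties went to the unscheduled reading, the totals would be 24.3%, 18.7% and 16.0%.

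**6. Cases that run the other way**

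- An unscheduled visit on Day 21 or 22, where treatment is deferred for a local skin reaction, is always preferred to the later treatment visit.
- An application on Day 74 or 75 puts an EOT reading on Day 84 at 84 - 74 = 10 or 84 - 75 = 9 days after it, and that reading is tabulated.
- In Days 95-157, if follow-up visits collect no vital signs (Table 2), a single unscheduled reading in a window is always selected. If they are collected on the planned day (6.2.6), it never is.

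**The case against.** The strongest reply is that little is lost.

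- **Extremes are shown.** SAP Section 5 summarises continuous variables with minimums and maximums as well as means. A reader might infer that averages over about 35 subjects would hide one or two abnormal values. They would not, for any reading that is in the table. What the table cannot show is how many subjects went from normal to abnormal.
- **Adverse events have their own route.** The TEAE tables in SAP 10.2 are not by visit, so the windows do not touch them. A vital-sign abnormality on Days 2-10 that is judged an adverse event would be counted. One not so judged stays in a listing.
- **Some unscheduled readings are selected.** A reader might infer that readings after application almost never reach the table, or that the table is bound to look clean. That is exact only for Days 2-10 and for a course exactly on schedule. With drift the share is 13% to 22%.
- **The readings may not exist.** Table 2 marks vital signs at unscheduled visits, but 6.2.4 and the matching lists in the synopsis and 6.1 omit them. The documents give no expected frequency of such visits.
- **There is no contradiction within SAP 10.6.** Change can be calculated for every post-baseline visit while the display is windowed.

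All five points stand, and they limit the consequence of the windows. None of them supplies the analysis that protocol 9.2.4 promises.

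**Conclusion.** The point holds in two parts. The SAP leaves out a vital-sign analysis that the protocol says will be done, and the protocol does not define it well enough to be run. This rests on the text alone. In addition, the efficacy windows exclude every Day 2-10 reading from the vital-sign table and admit later unscheduled readings only when they are closest to the planned day. For readings 1-10 days after an application, that is 0% on an exact schedule. With 17-25 day intervals it is about 13% (1-10 days) to 22% (1-3 days). Those percentages rest on equally likely intervals and reading days and on complete scheduled readings. They describe the selection rule and do not forecast how many readings will be lost. The documents do not support a claim that abnormal readings can appear only in listings. The matter deserves correction, but it does not put the study's main safety results in doubt.

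**What to change.** Keep the by-visit table and add the following to SAP 10.6, over all readings after the first application, including unscheduled and out-of-window ones:

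1. The number and percent of subjects who were normal at baseline and abnormal at any later reading, using limits for heart rate and temperature that the sponsor fixes in the SAP before the Day 84 analysis.
2. Each subject's highest temperature and highest and lowest heart rate, summarised.

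State that the Section 8 windows do not apply to these two summaries. Correct the reference to 4.3.1 in protocol 9.2.4 so that it points to where the limits are given. Reconcile Table 2 with protocol 6.2.4 and 6.2.6 on whether vital signs are taken at unscheduled and follow-up visits.

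Cost: one SAP paragraph and one extra table from data already collected, plus the protocol corrections. The vital-sign results may look slightly less favourable.
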